### 8.1. Hemodynamics

The hemodynamic parameters are listed here:

- Change from Day 1 baseline in seated systolic and diastolic blood pressures (BPs) and pulse to predose at Weeks 1, 4, 8, and 12
- Change from Day 1 baseline in orthostatic systolic and diastolic BPs and pulse to predose at Weeks 1, 4, 8 and 12
- For each study visit (Day 1, Weeks 1, 4, 8, 12), change from predose to each postdose time point of the same visit for seated systolic BP, diastolic BP and pulse.

Details about BPs and pulse assessment are included in [Section 7.4](#). An orthostatic measurement is derived by subtracting the seated measurement from the standing measurement.

Descriptive statistics will be tabulated for each hemodynamic parameter by treatment group. In addition, an analysis of covariance (ANCOVA) model will be fitted with change from baseline as dependent variable, treatment group, and stratification factor (HU use) as fixed effects, and corresponding baseline value as covariate, at each visit/time point. Pairwise contrasts will be used to compare each olinciguat group with the placebo group. Least-squares means (LSMs) for each treatment group, LSM differences between each olinciguat group and the placebo group, their corresponding 2-sided 95% CIs, and p-values will be presented. Example SAS code for ANCOVA model is shown below:

```
Proc mixed data = analysis_data;
  class stratum trt;
  model chg = base stratum trt;
  lsmeans trt/ cl diff;
run;
```

### 8.2. Vaso-occlusive Crisis (VOC)

#### 8.2.1. Primary Analysis of Exploratory VOC Parameters

Sickle cell-related pain crisis events will be documented as 'vaso-occlusive crises' (VOCs) on the AE eCRF page throughout the duration of the trial and adjudicated by an independent adjudicator. Only

This document is confidential.

adjudicated events that are deemed VOCs will be utilized in the endpoints defined below. An on-study sickle cell-related VOC is defined in [Section 5.2.5](#).

Acute chest syndrome, hepatic sequestration, splenic sequestration, priapism (each requiring a visit to a medical facility or documented telephone management) and death (except that due to suicide, accident, or other event clearly unrelated to the participant's medical condition) will also be considered VOCs, as well as subtypes of VOCs, for analysis purposes.

The exploratory VOC parameters are listed here:

- Time to first VOCs experienced during the Treatment Period, defined as (start date of VOC – the date of first dose of double-blind study drug + 1)
- Proportion of participants experiencing  $\geq 1$  VOC during the Treatment Period
- Annualized VOC rate during the Treatment Period, defined as  $365^*$  total number of events/ (last dose date – first dose date of double-blind study drug +1)

All 3 VOC parameters will be summarized by descriptive statistics by treatment group.

The time to first VOC will be summarized using Kaplan Meier method; the median event time (if appropriate) and 2-sided 95% CI for the median will be provided; 25% and 75% percentiles will also be presented. Additionally, the Kaplan Meier plots will be generated. For comparison between each olinciguat group and the corresponding placebo group, P-value will be generated from log-rank test.

Example SAS code for Kaplan Meier method is shown below:

```
Proc lifetest data=analysis_data;
  Time AVAL*CNSR(1);
  Strata trt;
Run;
```

For the proportion of participants experiencing  $\geq 1$  VOC (dichotomous endpoint), the proportions for each olinciguat treatment group and the corresponding placebo group will be compared using a Cochran-Mantel-Haenszel (CMH) test controlling for stratification factors (HU use). The difference in the proportions between each olinciguat group and the placebo group as well as the CMH estimates of odds ratio, risk difference, and p-values will be presented, along with the corresponding 2-sided 95% CIs.

Example SAS code for CMH model is listed as below:

```
Proc freq data=analysis_data;
  Tables stratum*trt*resp/ cmh alpha=0.05;
Run;
```

The annualized VOC rate will be analyzed using a stratified Wilcoxon rank sum test with HU use as the stratifying factor. The associated P-value will be reported.

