## 5. General Aspects for Statistical Analysis

### 5.1. General Methods

All applicable data will be summarized by randomized treatment arm, unless specified otherwise. For summary tables, unless otherwise noted, participants who were randomized to placebo will be summarized as:

- 1) PBO1: participants who were randomized to placebo under Protocol Amendment 3 or earlier,
- 2) PBO2: participants who were randomized to placebo under Protocol Amendment 4 or later, and
- 3) Overall: participants who were randomized to placebo under any version of the protocol.

The participants who were randomized to olinciguat dosing regimens will be summarized as:

- 1) 2 mg: participants who were randomized to 2 mg olinciguat dosing regimen under Protocol Amendment 3 or earlier,
- 2) 4 mg: participants who were randomized to 4 mg olinciguat dosing regimen under Protocol Amendment 3 or earlier,
- 3) 6 mg: participants who were randomized to 6 mg olinciguat dosing regimen under Protocol Amendment 3 or earlier, and
- 4) 18 mg: participants who were randomized to 18 mg olinciguat dosing regimen under Protocol Amendment 4 or later

For safety analysis, the data will be summarized by treatment arm actually received.

In addition, data will be summarized by scheduled visit and/or time-point where appropriate. Unscheduled or repeat assessments will not be included in summary tables, but will be included in listings.

Continuous variables will be summarized using descriptive statistics, including the number of observations (n), mean, standard deviation (SD), median, minimum, maximum and interquartile range (IQR). Categorical variables will be summarized using frequencies and percentages. Unless otherwise specified, percentages will be based on the total number of non-missing values.

Unless otherwise specified, all confidence intervals (CIs) will be 2-sided with a confidence level of 95%. No adjustments will be made for multiplicity.

All statistical analyses will be performed using SAS Version 9.4 or later for Windows.

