### 8.2.2. Sensitivity Analysis of Annualized VOC Rate

In addition, the following sensitivity analysis will be conducted for annualized VOC rate, using Safety Population.

This document is confidential.

- Summary using descriptive statistics for participants enrolled under Protocol Amendment 4 or later, with PBO2, and 18 mg olinciguat (split into 6 mg, 12 mg, 18 mg groups based on the participant's last up-titration).

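### The mean annualized VOC rate in the Safety Population can be driven by one short-exposure patient, and the rate's only inference is a P-value with no estimate or interval

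*SAP*

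**What the plan says.** SAP 8.2.1 lists three exploratory VOC parameters: time to first VOC, proportion with at least one VOC, and annualized rate. The third is the "Annualized VOC rate during the Treatment Period, defined as" 365 times the number of events divided by "last dose date – first dose date of double-blind study drug +1". Those dates belong to one participant, and a rank test needs one value per participant, so this is a per-patient ratio and not a pooled arm rate. No weighting, minimum exposure or cap is given.

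- **Summary.** "All 3 VOC parameters will be summarized by descriptive statistics by treatment group". Under SAP 5.1 this includes mean, SD, median, range and interquartile range, with no interval.
- **Test.** "The annualized VOC rate will be analyzed using a stratified Wilcoxon rank sum test with HU use as the stratifying factor". Then: "The associated P-value will be reported".
- **Sensitivity analysis (SAP 8.2.2).** Descriptive only: "Summary using descriptive statistics for participants enrolled under Protocol Amendment 4 or later, with PBO2, and 18 mg olinciguat", with the 18 mg arm split by the dose last reached.
- **Contrast within the same section.** For the proportion with a VOC, the difference is reported "as well as the CMH estimates of odds ratio, risk difference, and p-values will be presented, along with the corresponding 2-sided 95% CIs". The Kaplan-Meier median also gets a CI.
- **Populations.** SAP 8 runs the non-PRO pharmacodynamic analyses in the Safety Population (one dose suffices, SAP 4.3) and in the Evaluable Population (six weeks on drug required, SAP 4.6).
- **Already derived.** SAP 7.1 computes patient-years of treatment by group.

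**The concern.** In an unweighted mean of per-patient ratios, a patient with 7 days on drug counts as much as one with 85. Dividing one event by a very short span gives a very large rate, and the trial has arms of about 10 to 12 patients. The mean can then move far from the rate at which the arm as a whole had crises.

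The median offers little help. With Poisson counts over 85 days, more than half of patients have no VOC whenever the rate is below ln 2 × 365/85 = 2.98 per year, so both arm medians may well be 0. A reader would then look to the means for the size of effect. The P-value beside them does not correspond to a difference or ratio of means, and no interval would show how uncertain the contrast is. Frequency of crises is a named endpoint in protocol 4.2.1.2, and a Phase 2 reader planning a later trial needs an effect size with its uncertainty.

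**Working it through.** The plan gives no event count, power or assumed rate for VOCs to reproduce (SAP 3.4: the sample size was not set statistically). The checks apply the SAP formula directly.

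**Inputs.** About 48 patients at 3:1 (SAP 3.4, 3.5): 36 on 18 mg and 12 on the matched placebo (PBO2). About 40 at 1:1:1:1: 10 per arm, so overall placebo is 12 + 10 = 22. Full treatment is 85 days. Background rate is an assumption, varied from 1 to 10 per year, the range of prior crises allowed by inclusion criterion 6.

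**1. One VOC, annualized as 365/d.** 7 days: 52.1. 14 days: 26.1. 42 days: 8.7. 85 days: 4.3. In a 12-patient arm the 7-day patient adds 52.1/12 = 4.3 per year to the mean.

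**2. Share of the arm mean from one patient with one VOC in d days.** The other n − 1 patients complete 85 days at rate λ.

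- Mean = [(n − 1)λ + 365/d]/n
- Pooled rate = [(n − 1)λ × 85/365 + 1] / [((n − 1) × 85 + d)/365]
- For n = 12, λ = 1, d = 7: mean = (11 + 52.1)/12 = 5.26; share = 52.1/63.1 = 83%; pooled = 3.56/2.58 = 1.38

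| Arm, d | λ = 1 | λ = 4 | λ = 10 |
|---|---|---|---|
| PBO2 (12), 7 days: share | 83% | 54% | 32% |
| PBO2 (12), 7 days: mean v pooled | 5.26 v 1.38 | 8.01 v 4.36 | 13.51 v 10.31 |
| 18 mg (36), 7 days: share | 60% | 27% | 13% |
| PBO2 (12), 42 days: share | 44% | 16% | 7% |

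The 42-day row is the Evaluable minimum.

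**3. Worked example (assumed data).** On 18 mg, 9 of 36 patients have one VOC and all complete 85 days. On PBO2, 3 of 11 completers have one VOC, and the 12th patient has one VOC in 7 days.

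- SAP means: PBO2 (3 × 4.29 + 52.1)/12 = 5.42; 18 mg 9 × 4.29/36 = 1.07; ratio 0.20.
- Pooled rates: PBO2 365 × 4/(11 × 85 + 7) = 1.55; 18 mg 365 × 9/(36 × 85) = 1.07; rate ratio 0.69. SE of the log ratio = √(1/9 + 1/4) = 0.60; 95% CI 0.21 to 2.25.
- If the 12th patient has the same single VOC but completes 85 days: means 1.43 v 1.07; rate ratio 0.75 (0.23 to 2.44).
- The PBO2 median is 0 and the interquartile range 0 to 4.29 in both cases. The unstratified Wilcoxon P is 0.498 with 7, 14 or 42 days and 0.588 with 85.

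Shortening the exposure changes the ratio of means from 0.75 to 0.20, the pooled ratio from 0.75 to 0.69, and the rank test hardly at all.

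**4. Behaviour over repeated trials.** The simulation used 36 v 12 patients under equal rates of 1, 2 or 4 per year, gamma-Poisson counts, 10% or 20% early stopping and 4,000 trials per setting, all assumed. Stratified Wilcoxon type I error was 0.042 to 0.053. The PBO2 mean of ratios was essentially unbiased but more variable than the pooled rate (SD 0.85 v 0.70 at 1 per year with 20% stopping) and exceeded twice the pooled rate in about 1% to 2% of trials. At 10% stopping the extra variance ranged from (1.79/1.70)² − 1 = 11% to (0.76/0.67)² − 1 = 29%. With less overdispersion (0.5) and no stopping before Day 5 it was 6% to 14%.

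**5. Events available to a model.** A full PBO2 arm expects 12 × 85/365 = 2.8 events at 1 per year and 5.6 at 2 per year. At 1 per year the chance of none is e^−2.8 = 6% under Poisson counts, and about 8% to 11% in simulation with overdispersion and dropout.

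**The case against.** The strongest defence is that the plan already contains the safeguards.

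- The rank test limits what one extreme rate can do.
- SAP 5.1 requires the median and interquartile range beside the mean, and no text names the mean as the arm rate.
- The Evaluable analysis excludes anyone with under six weeks on drug, so a rate of 52 per year from one VOC cannot occur there.
- The proportion with a VOC has intervals, and the log-rank analysis can handle unequal follow-up.
- The table shells are not public, so event totals may already sit beside patient-years.
- A model on so few events is shaky. In simulation at 1 to 2 per year the negative binomial failed or reached zero dispersion in 36% to 55% of analysable 36 v 12 trials (43% to 63% at 10 v 22). Robust Poisson type I error was 5% to 8%. An exposure offset does not repair informative dropout either.

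Most of this stands, and it limits the point. Two parts do not answer it. The Evaluable Population is selected after randomization and leaves the Safety Population summary as it is. The proportion and time-to-first analyses do not estimate a rate of recurrent events. Wide intervals are no reason to omit them, because they show how little the data say.

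A reader might infer two stronger claims. One is that choosing the Wilcoxon test lets a single patient dominate the result. It is the opposite: ranks protect the P-value, and the fragility lies in the mean. The other is that unequal dropout biases the test. Even with an assumed 40% v 5% dropout at equal rates of 2 per year, the share with any VOC was 29% v 33% and type I error stayed near 5%. The documents give no dropout figure to support a larger effect.

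**Conclusion.** The point holds in a limited form. In the Safety Population the mean annualized VOC rate is sensitive to one short-exposure patient when the arm is small, exposure is about one to two weeks and the background rate is low. In both populations the rate has a P-value and no estimate or interval to go with it. The second part follows from the SAP text alone. The size of the first rests on assumed background rates and stopping times, and the 7-day patient is a deliberately unfavourable case.

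The median, interquartile range, Wilcoxon P-value and type I error are not undermined. In the Evaluable Population one VOC annualizes to at most about 8.7 per year. The endpoint is exploratory and the primary safety conclusion is untouched, so severity is low. This is a cheap improvement, not a correction of an invalid analysis.

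**What to change.** In SAP 8.2.1:

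1. Present the arm rate as total VOCs divided by total patient-years. Do not present the mean of per-patient rates as the arm rate.
2. Count events and exposure over the same window. At present events belong to the Treatment Period while the denominator ends at the last dose, so state how a VOC after early stopping is handled.
3. Add a rate ratio with 95% CI from a Poisson model with robust variance (or negative binomial where it converges), with log exposure as offset and treatment and HU use as factors. Specify in advance which model is the fallback.
4. If an arm has no events, give an exact or otherwise sparse-data-safe interval.
5. Keep the stratified Wilcoxon test.
6. Use the pooled rate in the SAP 8.2.2 dose split too, where subgroups may be smaller still.

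The cost is SAP wording and one model on data already derived; SAP 7.1 supplies patient-years. The downside is wide intervals and frequent use of the fallback with 10 to 12 patients per arm.

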5.1.3 Time-to-event Endpoints

For each treatment arm, Kaplan-Meier estimates will be used to estimate the survival function for time to first pain crisis. The median survival time for each treatment, as well as the Kaplan-Meier curves will be presented.

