### 3.4. Determination of Sample Size

For this Phase 2 study, an overall sample size of approximately 88 participants is planned. Of these participants, approximately 40 are expected to be randomized under Protocol Amendment 3 or earlier and approximately 48 participants are expected to be randomized under Amendment 4 and later (see [Section 3.5](#)). The sample size was determined outside of statistical considerations and is considered reasonable based on precedent set by prior studies of similar nature and design.

This document is confidential.

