### 3.5. Treatment Assignment

During the Run-in Period, all participants will receive placebo in a single-blind manner (Table 2).

Table 2. Dose Regimen During Single-blind Run-in Period

Dosage	Run-in (Day -17 or -14 to Day -1); QD Dose
placebo daily	1×matching placebo tablet
QD=once daily	

The Treatment Period is double blind and placebo controlled. Participants will be randomized through central randomization based on the protocol applicable at the time. The computer-generated randomization schedule will be prepared by an independent statistician not otherwise associated with the conduct of the study.

Under Protocol Amendment 3 or earlier, eligible participants will be stratified by hydroxyurea (HU) use and randomly assigned in a 1:1:1:1 ratio to 6 mg olinciguat, 4 mg olinciguat, 2 mg olinciguat, or placebo at Randomization Visit on Day 1 (Table 3).

Table 3. Dose Regimen by Treatment Period Week for Participants Randomized Under Amendment 3 and Earlier

Randomized Dose Level	Week 1=half dose		Weeks 2 to 12=full dose *	
	Dosage	QD Dose	Dosage	QD Dose
6 mg IW-1701	3 mg IW-1701 daily	1 × 3-mg IW-1701 tablet	6 mg IW-1701 daily	2 × 3-mg IW-1701 tablet
4 mg IW-1701	2 mg IW-1701 daily	1 × 2-mg IW-1701 tablet	4 mg IW-1701 daily	2 × 2-mg IW-1701 tablet
2 mg IW-1701	1 mg IW-1701 daily	1 × 1-mg IW-1701 tablet	2 mg IW-1701 daily	2 × 1-mg IW-1701 tablet
Placebo	Placebo daily	1 × matching placebo tablet	placebo daily	2 × matching placebo tablet

Under Amendment 4 and later, eligible participants will be stratified by HU use and randomly assigned in a 3:1 ratio to 18 mg olinciguat or placebo (Table 4).

Table 4. Dose Regimen by Treatment Period Week for Participants Randomized Under Amendment 4 and Later

Initial Dose Level (Day 1-Day 7)		Week 1 through Week 3 (Day 8-Day 28)		Week 4 through Week 12 (Day 29-Day 85)	
QD Dose	QD Dosage	QD Dose	QD Dosage	QD Dose	QD Dosage
6 mg IW-1701 daily	2×3-mg IW-1701 tablet	12 mg IW-1701 daily	4×3-mg IW-1701 tablet	18 mg IW-1701 daily	6×3-mg IW-1701 tablet
PBO daily	2×matching PBO tablet	PBO daily	4×matching PBO tablet	PBO daily	6×matching PBO tablet

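### The log-rank test for time to first VOC leaves out HU use, the randomisation stratum, and this endpoint has no between-arm effect estimate

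*SAP*

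**What the plan says.** **Randomisation.** SAP 3.5 stratifies by HU in both parts of the trial. Up to Amendment 3, "eligible participants will be stratified by hydroxyurea (HU) use and randomly assigned in a 1:1:1:1 ratio". From Amendment 4, "eligible participants will be stratified by HU use and randomly assigned in a 3:1 ratio to 18 mg olinciguat or placebo". Protocol 3.2 gives control of possible confounding by HU as the reason.

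**Time to first VOC.** Protocol 5.1.3 plans description only: "The median survival time for each treatment, as well as the Kaplan-Meier curves will be presented". SAP 8.2.1 plans Kaplan-Meier (KM) plots and quantiles ("the median event time (if appropriate) and 2-sided 95% CI for the median will be provided; 25% and 75% percentiles will also be presented") and adds a test: "For comparison between each olinciguat group and the corresponding placebo group, P-value will be generated from log-rank test". The example PROC LIFETEST code has treatment as its only STRATA variable. No hazard ratio, event-free proportion at a fixed day, or restricted mean is listed.

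**Contrasts.** SAP 8 names two sets: 18 mg against the placebo patients of Amendment 4 and later (PBO2), and each dose against all placebo patients combined.

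**Comparable analyses.** HU is in the ANCOVA (SAP 8.1), the CMH test on the proportion with at least one VOC and the Wilcoxon test on the annualised VOC rate (both SAP 8.2.1), and the MMRM (SAP 8.3.2).

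**Size.** "approximately 40 are expected to be randomized under Protocol Amendment 3 or earlier and approximately 48 participants are expected to be randomized under Amendment 4". SAP 3.4 adds: "The sample size was determined outside of statistical considerations and is considered reasonable based on precedent".

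**The concern.** Stratified randomisation balances HU across arms, so the true chance variation in the treatment comparison is smaller than an unstratified log-rank variance allows for. If HU predicts crises, the unstratified test rejects less than 5% of the time under the null and gives up some power. Protocol 1.1 says HU is indicated to reduce the frequency of painful crises, so it is a plausible predictor of this very endpoint. The SAP gives no reason for treating the log-rank test differently from its neighbours.

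The balance argument covers comparisons within one cohort. The combined placebo group mixes two separately randomised cohorts, and nothing guarantees that the HU mix matches across them. There an unstratified test can be confounded by HU, not merely conservative.

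Finally, a p-value from arms of about 10 to 36 patients says little without an estimate and interval. The listed quantiles describe each arm but do not compare arms, and some may not be estimable in 12 weeks.

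**Working it through.** The documents state no power, event count or effect size for this endpoint, so there is no planned figure to reproduce.

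**1. Arm sizes (SAP 3.4, 3.5).**
- Amendment 4 onward, 3:1: 48 × 3/4 = 36 on 18 mg and 48 × 1/4 = 12 on placebo.
- Amendment 3 or earlier, 1:1:1:1: 40/4 = 10 per arm.
- Overall placebo: 12 + 10 = 22, of whom 10 (45%) were not randomised alongside the 18 mg arm.

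**2. Size of the test.** Simulation with exponential first-event times, 36 v 12, half of each arm on HU, censoring at Day 85, no dropout, 4,000 runs, two-sided 5%. The HU effect and the rates are assumptions. Null case, 1.7 crises/year in the lower-risk stratum:

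| Hazard ratio between HU strata | Unstratified | HU-stratified |
|---|---|---|
| 2 | 4.8% | 5.5% |
| 3 | 3.4% | 5.4% |
| 4 | 2.5% | 5.6% |

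**3. Power at treatment hazard ratio 0.4** (unstratified v stratified, %), by where the assumed placebo rate of 2.2/year sits:

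| HU ratio | 2.2 is the lower rate | 2.2 is the mean rate | 2.2 is the higher rate |
|---|---|---|---|
| 2 | 44.1 v 45.6 | 35.5 v 36.8 | 29.6 v 30.1 |
| 3 | 44.8 v 50.6 | 33.2 v 36.1 | 26.6 v 28.2 |
| 4 | 43.4 v 53.6 | 32.0 v 36.2 | 25.5 v 27.1 |

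The gains are 1.5, 5.8 and 10.2 points in the first column, 1.3, 2.9 and 4.2 in the second, and 0.5, 1.6 and 1.6 in the third. With 2.2 as the geometric mean they are about 1, 3 and 6. With no HU effect, power is 38% v 37%. Repeat runs change the gains by up to about 1.5 points. In the last row of the first column the strata run at 2.2 and 2.2 × 4 = 8.8/year, a mean of 5.5/year, so the HU effect and the event count rise together.

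A second grid used 5,000 runs, arms of 36 v 12, 36 v 22 and 10 v 22, 84 days, non-HU rate 2 or 4/year and treatment hazard ratio 0.5 or 0.3:

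| HU hazard ratio | Gain from stratifying (points) |
|---|---|
| 1.0 | within ±0.5 |
| 0.56 | −0.1 to +1.8 |
| 0.33 | +0.9 to +4.8 |
| 0.20 | +1.6 to +6.7 |

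**4. What limits power most.** By Schoenfeld at 3:1, power = Φ(|ln HR| × √(0.1875 d) − 1.96). For HR 0.5, d = 20 gives Φ(1.342 − 1.96) = 27% and d = 30 gives Φ(1.644 − 1.96) = 38%. The event count matters more than the stratification.

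**5. Are the quantiles reached?** With a constant rate λ, quantile q is reached by Day 85 if λ ≥ −ln(1 − q)/(85/365):
- 25th percentile: ln(4/3)/0.2329 = 1.24/year
- median: ln 2/0.2329 = 2.98/year
- 75th percentile: ln 4/0.2329 = 5.95/year

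The chance of reaching each in the 12-patient placebo arm, with no dropout, is the binomial probability of at least 3, 6 or 9 events at p = 1 − exp(−λ × 85/365):

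| Rate/year | 25th | Median | 75th |
|---|---|---|---|
| 1 | 47% | 2% | 0% |
| 2 | 88% | 26% | 1% |
| 3 | 98% | 62% | 8% |
| 4 | ~100% | 85% | 24% |

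Entry requires 1 to 10 crises in the previous 12 months (inclusion criterion 6). The expected on-study rate is not given.

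**The case against.** The strongest reply is that little depends on this. The endpoint is exploratory, the sample size has no power basis, there is no multiplicity control, and the protocol planned no test here. Within a cohort the test does not inflate error. All of that stands, and it makes this a minor point.

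Four stronger readings are tempting, and the documents do not support them.

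- *The omission costs about ten points of power.* That needs strata at 2.2 and 8.8 crises/year. The documents give no HU effect, and both strata met the same entry rule of 1 to 10 crises, which may weaken HU as a predictor. Part of the gap also reflects a stratified test running at 5.4% to 5.6%.
- *The large power loss and the missing median occur together.* In the scenarios with 2.2/year as the lower rate, the placebo arm reaches its median in 66%, 86% and 93% of runs. Where the median is often missing, the loss is a few points.
- *The crisis analysis has no effect size.* That is true of this endpoint only. The proportion with at least one VOC gets an HU-controlled odds ratio and a risk difference with 95% CIs. The 25th percentile is usually reachable from 2/year, KM plots are planned, and the SAP itself makes the median conditional ("the median event time (if appropriate) and 2-sided 95% CI for the median will be provided").
- *The code gives only an omnibus test.* It is example code, and its data set is not specified. Run on two arms, it is the pairwise test that the text describes.

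**Conclusion.** The concern holds in a limited form. HU is missing from the log-rank test, contrary to the randomisation and to the SAP's other model-based or stratified comparisons, and time to first VOC has no between-arm estimate.

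For 18 mg v PBO2 the consequence is mild conservatism if HU is prognostic. The power loss ranges from none, through roughly 0.5 to 4 points with 2.2/year as the mean or higher stratum rate, to about 10 to 11 points at one extreme setting. These figures assume exponential times, half the patients on HU, no dropout, and HU effects that the documents do not supply.

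For the contrasts with overall placebo, HU balance is not guaranteed, so stratifying has a second purpose. It would remove imbalance in HU only, not other differences between the cohorts.

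The median and 75th percentile may not be reached, while the 25th usually will be from about 2/year. Severity is low. The case for change rests on consistency and the missing estimate more than on power.

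**What to change.** In SAP 8.2.1:

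1. State that the log-rank test is stratified by HU use and run separately for each contrast listed in SAP 8. In the example code, use `strata stratum / group=trt;` on each two-arm data set, and say that the data are subset in this way.
2. Add an HU-stratified Cox hazard ratio with 95% CI for each contrast.
3. Add KM event-free proportions with 95% CI by arm at fixed days, for example Days 29, 57 and 85. These remain available if an arm has too few events for a usable hazard ratio.
4. Keep the quantiles and report them where estimable.

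The cost is SAP wording and a few lines of SAS, with no new data. If HU turns out not to be prognostic, stratifying loses nothing material (37% v 38% power in the simulation).

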## 8. Pharmacodynamic (PD) Analyses

All PD analyses except the PRO analyses will be based on the Safety and Evaluable Populations. PRO analyses will be based on the ITT and Evaluable Populations. Listings will be provided for all PD-related data.

For the treatment comparisons by statistical modeling:

- comparisons between 18 mg olinciguat group vs. the matched placebo group (PBO2) enrolled under Protocol Amendments 4 and later
- comparisons between each olinciguat group (2 mg, 4 mg, 6 mg, and 18 mg) vs. the overall placebo group combined from all protocols

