### 8.3. Biomarkers

#### 8.3.1. Primary Analysis of Exploratory Biomarkers

Biomarker endpoints include the following:

- Change from baseline in hemoglobin (Hb) at Weeks 4, 8 and 12
- Proportion of patients with change from baseline in Hb  $>1$  g/dL at end of treatment
- Change from baseline in fetal hemoglobin (HbF) at Weeks 4, 8 and 12

Blood and urine samples for assessments of PD effects will be collected according to the applicable event schedule in Table 5a and 5b.

For each available biomarker, the observed value and the change from baseline (if applicable) will be summarized using descriptive statistics by treatment group and applicable time point.

The biomarkers of interest include LDH, reticulocyte count, bilirubin, Hb, HbF, haptoglobin, cystatin-C, urinary albumin and creatinine ratio (UACR), soluble E-selectin, soluble P-selectin, L-selectin, platelet monocyte aggregation, VCAM and ICAM.

Specifically, the following key biomarker responders for Hb and HbF will be summarized for each available visit and EOT.

1. Proportion of participants with increase from baseline in Hb  $>1$  g/dL
2. Proportion of participants with change from baseline in HbF  $>3\%$  points
3. Proportion of participants with increased change from baseline in HbF and HbF  $>8\%$

For each of the key biomarkers (Hb and HbF), the observed value and the changes from baseline will be summarized by treatment group and available visit. In addition, ANCOVA model mentioned in [Section 8.1](#) will be fitted to estimate the difference in change from baseline between each olinciguat group and the placebo group, for each available visit.

The proportion of biomarker responders specified above will be summarized by treatment group. In addition, a Cochran-Mantel-Haenszel (CMH) test (mentioned in [Section 8.2](#)) will be used to estimate the difference in the proportions for each olinciguat treatment group and the corresponding placebo group.

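### Yes/no endpoints: with contrasts of about 36 v 12 and 10 v 22 and no interval method named, large-sample CMH-type 95% CIs for the risk difference can under-cover, and odds ratios often fail when responses are uncommon

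*SAP*

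**What the plan says.** SAP 8.2.1 compares the proportion with at least one VOC by a CMH test stratified by HU use and states that "CMH estimates of odds ratio, risk difference, and p-values will be presented, along with the corresponding 2-sided 95% CIs". The example code is "Tables stratum*trt*resp/ cmh alpha=0.05". It asks for CMH output only, with no risk-difference or exact request. SAP 8.3.1 (Hb and HbF responders) and 8.4.1.1 (30% pain response) refer back to this test, which "will be used to estimate the difference in the proportions for each olinciguat treatment group and the corresponding placebo group". None of the three sections names a risk-difference interval, an exact method, or a rule for empty cells.

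Arm sizes follow from SAP 3.4 and 3.5. Of about 88 participants, "approximately 40 are expected to be randomized under Protocol Amendment 3 or earlier" and are "randomly assigned in a 1:1:1:1 ratio to 6 mg olinciguat, 4 mg olinciguat, 2 mg olinciguat, or placebo"; "approximately 48 participants are expected to be randomized under Amendment 4 and later" and are "randomly assigned in a 3:1 ratio to 18 mg olinciguat or placebo". SAP 8 plans "comparisons between 18 mg olinciguat group vs. the matched placebo group (PBO2) enrolled under Protocol Amendments 4 and later", and also each dose against placebo pooled over all amendments.

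**The concern.** A CMH test is a sound choice for a stratified two-arm comparison, but the estimates printed beside it rest on large-sample variances. With 12 placebo participants, no responders at all is a realistic result for an uncommon response. The odds ratio is then infinite or undefined, and a large-sample interval for the risk difference treats the placebo rate as known to be exactly zero. The study has no power or precision basis, so interval estimates carry most of its quantitative message on these endpoints. As written, the interval type would be left to the programmer, and the obvious choice is the one that does badly here.

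**Working it through.** **Inputs.** The plan states no event rate, precision or power figure, so there is none to reproduce. Arm sizes: 40/4 = 10 per arm up to Amendment 3; 48 × 3/4 = 36 on 18 mg and 48 × 1/4 = 12 on placebo from Amendment 4; pooled placebo 10 + 12 = 22. As a check, 40 + 48 = 88. Assumptions: half of each arm in each HU stratum, the same response rate in both strata, and rates of 5% to 50%.

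**Step 1: odds ratio.** Per stratum, let a of n respond on active and c of m on placebo, with N = n + m. The Mantel-Haenszel odds ratio is Σ a(m−c)/N divided by Σ c(n−a)/N. It is zero with no active responders, infinite with no placebo responders, and undefined with neither. For low rates, with q = 1 − p, the chance of failure is q^(placebo n) + q^(active n) − q^(total n). At p = 10%:
- 36 v 12: 0.2824 + 0.0225 − 0.0064 = 0.299, about 30%
- 10 v 22: 0.0985 + 0.3487 − 0.0343 = 0.413, about 41%
- 36 v 22: 0.0985 + 0.0225 − 0.0022 = 0.119, about 12%

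At 5% the figures are 61%, 73% and 43%; at 20% they are 7%, 11% and 0.8%.

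**Step 2: risk-difference interval.** The estimate is Σ w(a/n − c/m)/Σ w with w = nm/N, and the interval is the estimate ± 1.96 standard errors. Coverage is the total probability of all outcomes whose interval contains the true difference, by full enumeration. Each range runs from the Greenland-Robins to the Sato variance. The last column is the stratified Miettinen-Nurminen interval, as a range over the three contrasts.

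| Rate, both arms | 36 v 12 | 10 v 22 | 36 v 22 | Score interval |
|---|---|---|---|---|
| 5% | 93.9–94.0% | 97.3–98.3% | 95.8–96.1% | 96.9–97.5% |
| 10% | 84.8–85.0% | 90.9–92.9% | 92.9–93.2% | 95.4–96.9% |
| 20% | 89.3–90.0% | 88.9–90.2% | 93.4–94.0% | 95.2–95.4% |
| 30% | 90.8–91.9% | 90.8–91.8% | 93.3–93.7% | 95.0–95.2% |
| 50% | 91.5–92.5% | 91.0–92.2% | 93.3–93.7% | 94.7–95.1% |

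The 85% can be traced by hand. With no placebo responders, the large-sample interval excludes zero once 4 or more of 36 respond on active. At 10% that has probability 0.2824 × 0.4915 = 0.139, which is nearly all of the 15% non-coverage. The near-nominal 94% at 5% is no comfort: it counts as covering the trials with no responder in either arm (0.95^48 = 8.5%), where the interval has zero width at zero.

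With unequal rates on a 5–50% grid, the lowest coverage is 71% (36 v 12: placebo 10%, active 5%), 65% (10 v 22: placebo 5%, active 10%) and 88% (36 v 22). The grid medians are 91.7%, 91.7% and 93.7%. The score interval stayed between 94.2% and 98.8% in every scenario run.

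**Step 3: what a table could show.** Take 6/36 v 0/12, with 3/18 v 0/6 in each stratum. The difference is 16.7 points, with standard error √(0.1667 × 0.8333/36) = 6.2 points, so the large-sample CI is +4.5 to +28.8. CMH: Σ(a − expected) = 1.5, variance 1.027, chi-square 2.19, P = 0.14. The odds ratio is infinite. The stratified score CI is −9.5 to +32.3. The large-sample CI would exclude zero beside a P-value of 0.14.

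**Step 4: the P-value.** Under equal rates the size of the CMH test is 2.5% to 5.3% over the three contrasts, so the test needs no repair. At a difference of zero the score variance in a stratum with k responders, w²(k/N)(1−k/N)(1/n+1/m)·N/(N−1), reduces to nmk(N−k)/[N²(N−1)], the CMH variance. With these weights the score interval therefore excludes zero exactly when the CMH P-value, without continuity correction, is below 0.05. The table agrees: 96.9% coverage at 10% in 36 v 12 goes with a size of 3.1%.

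**Step 5: VOC.** Inclusion criterion 6 requires 1 to 10 crises in the prior year. Under an assumed constant rate r, P(at least one in 85 days) = 1 − exp(−85r/365), about 21% to 90%. At 1 to 5 crises a year (21% to 69%), the odds ratio fails in 0–10% of trials and Sato coverage is 90–94%. Only near 10 a year do failures rise, to 31%, 43% and 13% in 36 v 12, 10 v 22 and 36 v 22, with coverage of 85%, 93% and 93%.

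**The case against.** These endpoints are exploratory, there is no multiplicity claim, and the primary objective is descriptive safety. Hb and HbF are also analysed as continuous changes by ANCOVA and MMRM. Responder counts are tabulated by arm, so an empty cell would be visible. CMH follows Protocol 5.1.2. The code is offered only as an example, and no document gives a response rate, an HU share or an interval type. All of this stands. It lowers the weight of the point and makes every coverage figure conditional.

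Four stronger readings are tempting and not supported:
- That the odds ratio often fails for all these endpoints. At 20–50% in both arms it fails in at most 11% in any contrast, and VOC is the endpoint least likely to be affected. Moreover, 31 of the 41 points in 10 v 22 at 10% are odds ratios of exactly zero, which is a finite value though a poor summary.
- That the P-values are unreliable and need an exact test. Step 4 shows otherwise, and an exact conditional stratified test would cost power. In 10 v 22, at 40% v 10%, enumeration gives 54.9% for CMH and 39.2% for the exact test; at 50% v 10% it gives 73.7% and 59.9%.
- That the SAP commits to a Wald-type interval. It names none.
- That SAP Table 1 lists the HbF responders. It lists only the Hb responder; the word key for the HbF responders comes from 8.3.1.

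**Conclusion.** The point holds in a limited form. If a usual large-sample interval is used, risk-difference CIs labelled 95% would under-cover in 36 v 12 (about 85% at a 10% response, 89–92.5% at 20–50%) and in 10 v 22 (about 89–92% at 20–50%), with little effect in 36 v 22. At 10% the odds ratio would be zero, infinite or undefined in about 30% (36 v 12) to 41% (10 v 22) of trials. Responses that uncommon are plausible for the Hb and HbF responders and less so for VOC. The figures rest on assumed response rates, equal HU strata and full planned enrolment. The Evaluable Population would be smaller: at an assumed 29 v 10 and a 10% rate, 38% of odds ratios fail and coverage is 87.6%. Severity is low to moderate, because the endpoints are exploratory and the CMH P-values are sound.

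**What to change.** In SAP 8.2.1, 8.3.1 and 8.4.1.1:
- Make the HU-stratified risk difference, with a stratified Miettinen-Nurminen (score) 95% CI, the reported effect. State the Mantel-Haenszel stratum weights, so that interval and CMH P-value agree about zero.
- Correct the example code so that it requests this interval, and confirm that the routine used gives the stratified version named.
- Keep the CMH P-value.
- Show the odds ratio with an exact CI, or print 'not estimable' when an empty cell makes it zero, infinite or undefined. A score interval for the difference does not cure that.

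The cost is a few lines of SAP text and programming before database lock, with no new data. The downside is somewhat wider intervals.
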